## **10.5 Safety**

The safety and tolerability assessments are listed below:

- AEs and SAEs
- hypotension
- Angioedema
- Laboratory values
- Hyperkalemia
- Renal dysfunction

The assessment of safety will be based primarily on the frequency of adverse events, SAEs, and laboratory abnormalities. Other safety data will be summarized as appropriate.

The incidence of treatment-emergent adverse events (new or worsened) will be summarized by primary system organ class, preferred term, severity, and relationship to study drug. In addition, the incidence of death, SAEs, and AEs leading to discontinuation will be summarized separately by primary system organ class and preferred term.

Laboratory data will be summarized by presenting shift tables using extended normal ranges (baseline to most extreme post-baseline value), by presenting summary statistics of raw data and change from baseline values and by the flagging of notable values in data listings.

We will use Fisher's exact test to compare rates of Safety outcomes.

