## Protocol synopsis

**Protocol title:** Angiotensin receptor-neprilysin inhibitor (ARNI, Sacubitril/Valsartan) versus Enalapril in patients with acute anterior wall ST-elevation myocardial infarction after emergency PCI: a prospective randomized trial

**Rationale & background information:** Ventricular remodeling after acute myocardial infarction (AMI) is closely related to the occurrence of heart failure (HF). Despite opening the infarct-related artery as early as possible and using the best medical treatment, about 41.5% of STEMI patients still have ventricular remodeling at 6 months. LV remodeling is a complex pathophysiological process that develops gradually over time. Neuroendocrine hormones, persistently activated, play an important role in this process, except for the extent of initial myocardial injury, and are closely associated with the progression of heart failure (HF).

In recent years, the application of Sacubitril/Valsartan (Sac/Val) has brought bright sight to patients with heart failure. Sac/Val can inhibit the activation of endorphinase and renin-angiotensin-aldosterone system (RAAS) at the same time. According to PARADIGM-HF study and other researches, Sac/Val could reduce cardiovascular mortality and re-admission rate of heart failure patients who had a reduced heart ejection fraction. Whether the initiation of Sac/Val immediately is effective and safe among patients with acute anterior STEMI (a high-risk factor for HF) is unknown. Therefore, the purpose of this study is to evaluate the safety and effectiveness of immediate initiation of Sac/Val in patients with acute anterior STEMI after PCI.

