## **1 Background**

Angiotensin receptor-neprilysin inhibitor (ARNI, Sacubitril/Valsartan) is superior to angiotensin-converting enzyme inhibitors (ACEI) on cardiac remodeling in patients with heart failure (HF). However, there is little data describing the effects of sacubitril/valsartan in patients with acute anterior ST-segment elevation myocardial infarction (STEMI). The objective is to assess the safety and efficacy of sacubitril/valsartan compared with Enalapril in patients with acute anterior STEMI after PCI.

This study is a single center, prospective, randomized, double-blind trial, planning to recruit patients with acute anterior STEMI at the Second Affiliated Hospital of Nanchang University. Patients are randomly assigned 1:1 to in-hospital initiation of sacubitril/valsartan and enalapril. The starting dose during the in-hospital initiation phase and all subsequent dose changes during the titration period is selected using a dose titration algorithm (Figure 1). Patients are followed up at 4, 12, and 24 weeks after discharge from the hospital, blood test and echocardiograph are performed. The primary efficacy outcomes are the changes in NT-proBNP concentrations and in echocardiographic parameters (LVEF, LVEDV, LVESV) from baseline through weeks 4, 12 and 24. Secondary outcomes include the incidence of a composite of death, reinfarction, hospitalization for heart failure or outpatient heart failure, arrhythmia, stroke. Safety endpoints are the incidence of angioedema, hypotension, renal insufficiency, and hyperkalemia.

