## **10.6 Sample size calculation**

The targeted sample size mainly is driven by the LVEF of the primary outcomes. Assuming that the increase in LVEF is  $3\% \pm 6\%$ , the patients are included in the ratio 1:1 when  $\alpha=0.05$  and the test power is 80%, and the sample size for each group is predicted to be 64 cases. Taking into account the loss to follow-up rate of 10%, it is estimated that a total of 142 patients will be needed

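### Safety versus enalapril is part of the stated purpose, but the only between-arm safety method fixed is Fisher's exact test, which is weak at about 71 per arm and gives no estimate of the difference

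*Protocol*

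**What the plan says.** **Purpose.** The protocol synopsis (rationale) says that "the purpose of this study is to evaluate the safety and effectiveness of immediate initiation of Sac/Val" after PCI. Section 1 (Background) makes the question comparative: "The objective is to assess the safety and efficacy of sacubitril/valsartan compared with Enalapril in patients with acute anterior STEMI after PCI". It then names four outcomes: "Safety endpoints are the incidence of angioedema, hypotension, renal insufficiency, and hyperkalemia". The formal primary and secondary objectives (sections 3.1 and 3.2) and section 2 cover only NT-proBNP, echocardiography and cardiovascular events; they do not mention safety.

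**Analysis.** Section 10.5 opens with a descriptive basis: "The assessment of safety will be based primarily on the frequency of adverse events, SAEs, and laboratory abnormalities". It adds adverse-event tables, separate summaries of deaths, SAEs and discontinuations, shift tables and flagged laboratory values. It ends with the only between-arm method: "We will use Fisher's exact test to compare rates of Safety outcomes". The synopsis repeats that sentence. By contrast, section 10.4.2 specifies hazard ratios with 95% confidence intervals for the secondary efficacy outcome.

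**Size.** Section 10.6 says: "The targeted sample size mainly is driven by the LVEF of the primary outcomes". It assumes 3 points with an SD of 6, "and the test power is 80%, and the sample size for each group is predicted to be 64 cases", and 142 in total after 10% loss. No expected rate is given for any safety outcome.

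**The concern.** A p-value alone does not say how large a difference in harm the data allow. In a trial sized on a continuous echocardiographic outcome, a test of event rates will often be non-significant even when harm really is more frequent in one arm. If the p-value is the only comparative result the protocol plans, a report that finds no significant difference in hypotension, renal insufficiency, hyperkalemia or angioedema could be taken as an answer to the safety question, while the same data remain compatible with a clinically relevant excess. For angioedema the test is close to uninformative at this size.

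**Working it through.** **Inputs.** From section 10.6: LVEF difference 3 points, SD 6, alpha 0.05, power 80%, 1:1 allocation, 64 per arm, 10% loss, 142 in total (71 per arm). Section 10.1 analyses all randomized patients; it refers to efficacy variables, and no separate safety set is described, so 71 per arm is taken as the most favourable case. *Assumptions:* two-sided testing at 0.05 (section 10.5 does not state sidedness or level), and the enalapril-arm event rates, which the protocol does not give.

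**Step 1: the plan's own figure.** n per arm = 2 × (1.960 + 0.842)² × 6² / 3² = 62.8, so 63 by the normal approximation. The t-based calculation gives 64 (power 80.1%). For losses, 128 / 0.90 = 142.2, stated as 142. The sample size is reproduced, and it contains no safety input.

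**Step 2: chance of missing a doubling.** Let X and Y be the event counts in the two arms, binomial with n = 71 and rates p and 2p. Power is the sum of P(X = i) × P(Y = j) over all pairs (i, j) whose two-sided Fisher p-value is at most 0.05. The miss rate is 1 minus power.

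| Assumed rates | Miss, 71 per arm | Miss, 64 per arm |
|---|---|---|
| 2% vs 4% | 98% | 99% |
| 5% vs 10% | 88% | 90% |
| 10% vs 20% | 69% | 73% |
| 15% vs 30% | 50% | 55% |
| 20% vs 40% | 31% | 37% |
| 25% vs 50% | 17% | 20% |
| 30% vs 60% | 6% | 9% |

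For comparison, 80% power to detect a doubling needs about 435 per arm at 5%, 199 at 10% and 82 at 20% (normal approximation, no continuity correction).

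**Step 3: rare events (angioedema).** With no events on enalapril, 5/71 vs 0/71 gives p = 0.058 and 6/71 vs 0/71 gives p = 0.028. Six events (6/71 = 8.5%) are therefore needed for significance. At an assumed true rate of 2%, the probability of at least 6 events in 71 is 0.003. If an arm has no events, the upper limit of the exact 95% interval is 1 - 0.025^(1/71) = 5.1%.

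**Step 4: what an interval adds.** Take 14/71 (19.7%) vs 7/71 (9.9%) as an illustration. Fisher p = 0.155. The risk difference is 9.9 points. The Wilson limits are 12.1% to 30.4% and 4.9% to 19.0%. The Newcombe limits follow:

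- lower: 9.9 - √[(19.7 - 12.1)² + (19.0 - 9.9)²] = about -2.0 points
- upper: 9.9 + √[(30.4 - 19.7)² + (9.9 - 4.9)²] = about 21.7 points

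The p-value reports only non-significance. The interval shows that an excess of more than 20 points is not ruled out.

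**Step 5: expected width.** With equal true rates and 71 per arm, the 95% half-width is about 1.96 × √[2p(1 - p)/71]: 7.2 points at p = 5%, 9.9 at 10% and 13.2 at 20%.

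**The case against.** Fisher's exact test is valid for small counts, and low power for safety is normal in a trial sized on efficacy. Section 10.5 rests safety primarily on frequencies, so a doubling would be visible in the tables, and a reader could compute an interval from the counts. An external data monitoring committee (section 8.4) and dedicated angioedema reporting (section 8.5) also watch safety. Intervals may be specified in a statistical analysis plan that is not shown. The proposed intervals will be wide and come with no threshold, so they give no decision rule either.

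Much of this stands. It means that the fault is neither the choice of test nor the sample size, and that the p-value is not the sole source of safety information. It does not remove the point. The protocol itself chose a comparative method for a comparative question, and that method yields only a p-value. A wide interval is also useful, because it shows how little has been excluded.

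A reader might infer more than the documents support:

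- *That the trial will treat non-significance as proof of safety.* No section says so, and the text speaks only of evaluating or assessing safety.
- *That a non-inferiority margin is missing.* The protocol makes no non-inferiority or equivalence claim on safety, and its formal objectives leave safety out.
- *That a doubling would most likely be missed whatever the event rate.* That holds only for assumed enalapril rates below about 15%. At 20% the test detects a doubling 69% of the time, and at 25% about 83%.

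**Conclusion.** The point holds in limited form, as an inexpensive improvement that should be made. Safety against enalapril is a stated purpose, and the only between-arm safety method that the protocol fixes is a bare significance test, alongside descriptive frequencies. Under assumed enalapril rates of 5% to 20%, and with all 71 per arm analysed, that test misses a true doubling 88% to 31% of the time. The miss rate is 98% at an assumed 2% and about 17% at 25%. The range depends wholly on the assumed rates and on two-sided testing at 0.05. A non-significant result would therefore be weak evidence on comparative safety. That it might be misread as reassurance is a risk that the wording leaves open; the protocol does not instruct it.

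**What to change.** In section 10.5 and the synopsis, replace the Fisher sentence with text to this effect:

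- For hypotension, renal insufficiency, hyperkalemia and angioedema, the between-arm safety result is the risk difference (sacubitril/valsartan minus enalapril) with a two-sided 95% confidence interval, for example Newcombe's.
- Where an arm has no events, the upper limit of its exact 95% interval is also given.
- Fisher p-values are descriptive, and a non-significant p-value is not evidence of comparable safety.

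In section 10.6, add that the sample size was not chosen to detect or to exclude differences in safety outcomes.

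The cost is a few sentences and a few lines of analysis code, with no extra patients or data. The small downside is that the intervals will be wide (about ±10 points at a 10% rate), so the safety conclusion will be more cautious.

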## **10.6 Sample size calculation**

The targeted sample size mainly is driven by the LVEF of the primary outcomes. Assuming that the increase in LVEF is  $3\% \pm 6\%$ , the patients are included in the ratio 1:1 when  $\alpha=0.05$  and the test power is 80%, and the sample size for each group is predicted to be 64 cases. Taking into account the loss to follow-up rate of 10%, it is estimated that a total of 142 patients will be needed

## **10.7 End of the study**

The actual trial time will depend on the end of the last patient follow-up time. As planned, it is expected to be about 18 months: a recruitment period of 12 months and a minimal follow up of 6 weeks.

# **11 Ethical considerations**

## **11.1 Regulatory and ethical compliance**

This clinical study was designed and shall be implemented and reported in accordance with the ICH Harmonized Tripartite Guidelines for Good Clinical Practice, with applicable local regulations, and with the ethical principles laid down in the Declaration of Helsinki.

## **11.2 Informed consent procedures**

Eligible patients may only be included in the study after providing written (witnessed, where required by law or regulation), Research Ethics Board approved informed consent. Informed consent must be obtained before conducting any study-specific procedures (i.e. all of the procedures described in the protocol). The process of obtaining informed consent should be documented in the patient source documents.

Women of child bearing potential should be informed that taking the study medication may involve unknown risks to the fetus if pregnancy were to occur during the study and agree that in order to participate in the study they must adhere to the contraception requirement for the duration of the study. If there is any question that the patient will not reliably comply, they should not be entered in the study.

## **11.3 Responsibilities of the investigator and REB**

The protocol and the proposed informed consent form must be reviewed and approved by Ethics Committee of the Second Affiliated Hospital of Nanchang University before study start. Prior to study start, the investigator is required to sign a protocol signature page confirming his/her agreement to conduct the study in accordance with these documents and all of the instructions and procedures found in this protocol and to give access to all relevant data and records to research team and investigators as required.

## **11.4 Publication of study protocol and results**

Research team assures that the key design elements of this protocol will be posted in a publicly accessible database such as Chinese clinical trial Registry.

## **12 Protocol adherence**

Investigators ascertain they will apply due diligence to avoid protocol deviations. Under no circumstances should the investigator request approval of a protocol deviation, as no authorized deviations are permitted. If the investigator feels a protocol deviation would improve the conduct of the study this must be considered a protocol amendment, and unless such an amendment is agreed upon by research team and approved by the Ethics Committee of the Second Affiliated Hospital of Nanchang University it cannot be implemented.

## 14 Appendix 1: Clinically notable laboratory values and

### vital signs

Clinically notable laboratory abnormalities for selected tests based on a percent change from baseline:

#### Hematology

RBC count	>50% increase, >20% decrease
Hemoglobin	>50% increase, >20% decrease
Hematocrit	>50% increase, >20% decrease
WBC count	>50% increase, >50% decrease
Platelet count	>75% increase, >50% decrease

#### Blood Chemistry

ALT (SGPT)	>150% increase
AST (SGOT)	>150% increase
BUN	>50% increase

Creatinine	>50% increase
Total bilirubin	>100% increase
CPK	>300% increase
Alkaline phosphatase	>100% increase
Potassium	>20% increase, >20% decrease
Chloride	>10% increase, >10% decrease
Calcium	>10% increase, >10% decrease
Uric acid	>50% increase

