### 5.2 Exclusion criteria

1. Previous history of myocardial infarction or chronic heart failure
2. Previous PCI, coronary artery bypass graft (CABG), implantation of other heart assist devices or heart transplantation
3. Known history of angioedema
4. Previous history of intolerance to recommended target doses of ACEIs or ARBs.
5. Previous use of sacubitril/valsartan
6. History of hypersensitivity or contraindications to the study drugs including ACEI, ARB, sacubitril/valsartan
7. Symptomatic hypotension and/or a SBP  $< 100$  mmHg at Visit 1 (screening), Visit 2 (randomization), Visit 3 (outpatient dose titration) or Visit 4 (follow-up)
8. Estimated GFR  $< 30$  mL/min/1.73m^2 as measured by the simplified MDRD formula at Visit 1 (screening), Visit 2 (randomization), Visit 3 (outpatient dose titration) or Visit 4 (follow-up) or  $> 25\%$  decline in eGFR between Visit 1 and Visit 2 or between Visit 2 and Visit 3 or between Visit 3 and Visit 4
10. Serum potassium  $> 5.2$  mmol/L at Visit 1 (screening), Visit 2 (randomization), Visit 3 (outpatient dose titration) or Visit 4 (follow-up)
11. History of severe pulmonary disease
12. Diagnosis of peripartum or chemotherapy induced cardiomyopathy prior to Visit 1
13. Documented untreated ventricular arrhythmia with syncopal episodes within the 3 months prior to Visit 1
14. Symptomatic bradycardia or second or third degree heart block without a pacemaker
15. Presence of hemodynamically significant mitral and/or aortic valve disease, except mitral regurgitation secondary to left ventricular dilatation

16. Presence of other hemodynamically significant obstructive lesions of left ventricular outflow tract, including aortic and sub-aortic stenosis

17. Life expectancy is less than 1 year

18. Any surgical or medical condition which might significantly alter the absorption, distribution, metabolism, or excretion of study drugs, including but not limited to any of the following

- History of active inflammatory bowel disease during the 12 months before Visit 1.
- Current duodenal or gastric ulcers during the 3 months prior to Visit 1
- Evidence of hepatic disease as determined by any one of the following: AST or ALT values exceeding 2 x ULN at Visit 1, history of hepatic encephalopathy, history of esophageal varices, or history of portacaval shunt
- Active treatment with cholestyramine or colestipol resins

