## **15 Appendix 2: Treatment guidelines for hyperkalemia**

### **(serum potassium greater than or equal to 5.3 mmol/L)**

#### **General principles**

Elevation of potassium levels above the predefined values should be repeated and confirmed before any action is taken. Any patient who experiences a potassium level 5.5 mmol/L confirmed by repeated testing during the screening period should be withdrawn from the study. Any patient with a serum potassium > 5.3 mmol/L after randomization requires regular, repeated checks of potassium concentration (beyond that prescribed in the protocol) until it is clear that the potassium concentration is stable and not rising into the range of concern (5.5 and < 6.0 mmol/L) or potential danger (6.0 mmol/L).

Investigators should not randomize a patient with a serum potassium 5.5 mmol/L during the screening period. Patients with elevated potassium value will be managed according to the corrective actions outlined below.

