**Serum potassium greater than or equal to 6.0 mmol/L**

- Immediately discontinue study drug
  - Confirm potassium concentration in a non-hemolyzed sample
  - Urgently evaluate patient and treat hyperkalemia as clinically indicated
  - Apply all measures outlined for serum potassium  $> 5.3$  and  $< 6.0$  mmol/L
- No resumption of study drug without individualized case discussion with and permission from his/her designee.

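### The Appendix 1 potassium flag uses percent change alone and misses values on which Appendix 2 acts; separately, the protocol gives two potassium limits for randomization and two lower bounds for hyperkalemia.

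*Protocol*

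**What the plan says.** Section 7.5.4 of the protocol sends the reader to Appendix 1 for the definition of a notable laboratory finding. Appendix 1 introduces its list as "Clinically notable laboratory abnormalities for selected tests based on a percent change from baseline", and the potassium line reads "Potassium >20% increase, >20% decrease". It gives no absolute potassium limit.

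The flag has two stated uses. Under Section 7.5.4 the investigator must comment on a notable value and arrange further tests as judged appropriate. Under Section 10.5 laboratory data are summarized by shift tables, by summary statistics and "by the flagging of notable values in data listings".

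Hyperkalemia is a named safety outcome. Section 1 states: "Safety endpoints are the incidence of angioedema, hypotension, renal insufficiency, and hyperkalemia". Section 10.5 lists it separately from laboratory values and adds: "We will use Fisher's exact test to compare rates of Safety outcomes".

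Appendix 2 works on absolute potassium. Its title covers values of 5.3 mmol/L or more, but its text and first band start above 5.3. The bands are above 5.3 to 5.5, above 5.5 to below 6.0, and 6.0 or more. In the last, the first instruction is "Immediately discontinue study drug".

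On entry, exclusion criterion 10 (Section 5.2) bars "Serum potassium $> 5.2$ mmol/L at Visit 1 (screening), Visit 2 (randomization") and at the later visits. Appendix 2 says: "Investigators should not randomize a patient with a serum potassium 5.5 mmol/L during the screening period".

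**The concern.** A rule based only on relative change depends on where the patient starts. The higher the baseline, the higher the absolute potassium must climb before it is called notable, so the flag is least sensitive in patients who begin closest to the levels Appendix 2 treats as dangerous. A value serious enough to stop study drug under one appendix can be unremarkable under the other. At stake are the prompt to the investigator and the completeness of the flagged listing for a safety outcome that matters when two drugs acting on the renin-angiotensin system are compared.

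The other two discrepancies concern consistency. A site that consults Appendix 2 about randomization meets a looser limit than the one in the exclusion criteria. A patient at exactly 5.3 is inside the scope of the Appendix 2 title but outside its first band.

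**Working it through.** The protocol gives no figure of its own to reproduce here. The check applies the Appendix 1 rule to eligible baselines and compares the result with Appendix 2.

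**Inputs**
- Upward flag: change strictly greater than 20% (Appendix 1).
- Baseline: last non-missing value before the first randomized dose (Section 10.2).
- Highest eligible baseline: 5.2 mmol/L, since exclusion 10 bars anything above it at Visits 1 and 2.
- Absolute levels: 5.3, 5.5 and 6.0 mmol/L (Appendix 2).

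**Formula.** A post-baseline value is flagged upward only if value > 1.2 × baseline. A given level is therefore flagged only if baseline < level / 1.2.

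- 5.3 / 1.2 = 4.42, so 5.3 is missed from baseline 4.5 upward (potassium to one decimal).
- 5.5 / 1.2 = 4.58, so 5.5 is missed from baseline 4.6 upward.
- 5.6 / 1.2 = 4.67, so 5.6, which lies in the second Appendix 2 band, is missed from baseline 4.7 upward.
- 6.0 / 1.2 = 5.00, so 6.0 is missed at baselines 5.0, 5.1 and 5.2.

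| Baseline | Flagged only above | Is 5.5 flagged? | Is 6.0 flagged? |
|---|---|---|---|
| 4.5 | 5.40 | yes (+22.2%) | yes (+33.3%) |
| 4.6 | 5.52 | no (+19.6%) | yes (+30.4%) |
| 4.9 | 5.88 | no (+12.2%) | yes (+22.4%) |
| 5.0 | 6.00 | no (+10.0%) | no (+20.0%, not more than 20%) |
| 5.1 | 6.12 | no (+7.8%) | no (+17.6%) |
| 5.2 | 6.24 | no (+5.8%) | no (+15.4%) |

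From baseline 5.2, nothing up to and including 6.24 is flagged.

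**Entry limits.** Exclusion 10 bars values above 5.2. In the text available, the comparison sign before 5.5 in Appendix 2 is missing, which may be a loss in conversion and is not counted as an error. If the sign is ≥, values of 5.3 and 5.4 are barred by exclusion 10 but not by Appendix 2. If it is >, the same holds for 5.3, 5.4 and 5.5. The values 5.3 and 5.4 conflict under either reading.

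**Lower bound in Appendix 2.** Title: 5.3 or more. Text and first band: above 5.3. The two differ at exactly 5.3.

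**The case against.** The strongest reply is that Appendix 1 is a listing flag and not the definition of hyperkalemia. That is correct. A reader might infer that the hyperkalemia rate compared by Fisher's exact test is built on the 20% rule and so is distorted by baseline potassium. The protocol does not support this: Section 10.5 lists hyperkalemia and laboratory values as separate items and nowhere ties the test to flagged values. That the protocol states no case definition is not the complaint either, since a statistical analysis plan may supply one.

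A reader might also infer that a potassium of 6.0 goes unnoticed. It does not. Section 10.5 calls for shift tables from baseline to the most extreme value and for summaries of raw data. Sections 7.5.4 and 8.1 make an abnormality an adverse event if it causes symptoms, is clinically significant or needs treatment. Appendix 2 requires action whatever Appendix 1 says. This cover is not complete at lower levels: an asymptomatic rise from 4.8 to 5.5 is not flagged and becomes an adverse event only by judgment or if treated, and the limits of the extended normal ranges are not stated.

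A third tempting reading is that Appendix 2 lets in patients whom exclusion 10 bars. It does not. Section 4.2.1 admits only patients with the values required by the entry criteria, Section 4.2.2 requires that no exclusion criterion be met, and Section 12 allows no authorized deviation. A prohibition at 5.5 is not permission at 5.4. What remains is a second, looser limit that should not be there unreconciled.

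Finally, the percent rule also flags changes such as 3.6 to 4.4 (4.4 / 3.6 = 1.222, +22.2%). Calling these normal assumes a reference range that the protocol does not give, and extra entries in a listing do little harm. A relative flag is a reasonable complement to an absolute one. The weakness is that it stands alone.

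**Conclusion.** The point holds within limits. The only notable-potassium rule in the protocol misses 6.0 mmol/L at eligible baselines of 5.0 to 5.2, and misses 5.5 from about 4.6 upward, although Appendix 2 acts at these levels. What is lost is the investigator-comment prompt and the mark in the listing. Detection by other routes and clinical management under Appendix 2 are not lost. The 6.0 case is narrow: it needs a baseline of at least 5.0, and the missed range ends at 6.24. The 5.5 case covers a wider span of baselines.

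The two contradictions, 5.2 against 5.5 for randomization and ≥5.3 against >5.3 within Appendix 2, are plain on the page. Neither changes who may properly be randomized if the entry criteria are followed.

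The conclusion assumes potassium recorded to one decimal and a baseline that satisfies exclusion 10. How many patients would be affected, and whether the between-arm comparison would move, cannot be computed because the protocol gives no potassium distribution.

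**What to change.** - In Appendix 1 and Section 10.5, keep the percent-change flag and add an absolute post-baseline potassium flag using the protocol's own Appendix 2 bands, once those are reconciled.
- In Section 10.5, report the number of patients per arm reaching each band, compared by Fisher's exact test as already planned for safety outcomes. Count local and unscheduled values as well as central-laboratory ones: Section 7.5.4.3 allows local potassium checks during titration and follow-up, mainly at unscheduled visits, and a central-only count could drop events found there.
- Reconcile the screening and randomization limit in Appendix 2 with exclusion criterion 10, so that one limit applies.
- Make the Appendix 2 title and text agree on the lower bound.

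Which limits are clinically right is for the investigators to decide, and this review takes no position on it. The cost is wording in Appendix 1, Appendix 2 and Section 10.5, plus one more table. No new measurement is needed, because potassium is already taken at Visits 1 to 4.
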